8. STUDY PROCEDURES

8.1. Investigation outline

Each test person will participate in three lab visits and a field-trial period.

Pre-screening

Adult patients who are already implanted with a BAHS are considered candidates for the study (see inclusion criteria).

- The audiologist will pre-screen the database for suitable candidates that meet the inclusion criteria.
- The test person is contacted over the phone or through an email or letter.
- The test person is informed about the study.
- The test person is given time to consider his/her participation and ask questions.
- The test person is given the opportunity to either accept or decline the offer to participate in the study.
- If a test person accepts, the 1st visit is scheduled. The patient is reminded that no caffeine should be taken on the 6 hours before Visit 1.

Visit 1

- The test person is informed about the study including all study related visits.
- Detailed information and instructions about the study.
- Consent form is signed.
- The test person's demographical data as well as their personal data and patients' characteristics are registered in the CRF.
- Fitting of Ponto 4 is performed (OSN ON, OSN OFF, OSN Auto)
- Pupillometry during a speech-in-noise test is performed (training, OSN ON, OSN OFF, OSN Auto – see Figure 1).
- All subjects fill in the SSQ and NfR questionnaires in relation to their own device (reference device).

Visit 2: 1-10 days after Visit 1

- Get Ponto 4 ready for testing (OSN ON, OSN OFF, OSN Auto)
- Pupillometry during a speech-in-noise test is performed (training, OSN ON, OSN OFF, OSN Auto – see Figure 1).
- The test person is instructed on the usage of Ponto 4 (including getting the Oticon ON app on their smartphone, or offer a Connectclip)
- SSQ questionnaire is handed out.

Phone reminder: 4-5 weeks after Visit 2

- The test leader reminds the patient to fill out the SSQ questionnaire in relation to the performance with Ponto 4 in the first month of trial. The patient will then put the questionnaire in an envelope and bring it at Visit 3.

Visit 3: 12-15 weeks after Visit 2

- Hand in SSQ questionnaire filled out at home.
- Pupillometry during a speech-in-noise test is performed (training, OSN OFF, OSN Auto).
- Audiometry is performed (AC, masked BC).
- Sound-field audiometry is performed with Ponto 4.
- All subjects fill in the SSQ and NFR questionnaires in relation to Ponto 4.
- All subjects fill in the preference questionnaire.

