7.1.2 Secondary endpoints

- Difference in peak pupil dilation (PPD) between OSN ON and OSN OFF across SNRs.
- Difference in speech recognition scores between OSN ON and OSN OFF across SNRs.
- Difference in overall pupil dilation, as calculated via Growth Curve Analysis, between OSN ON and OSN OFF across SNRs.
- Difference in overall pupil dilation between OSN Auto and OSN OFF at +4 dB SNR (measured at visits 1 or 2), as calculated via Growth Curve Analysis.
- Difference in overall pupil dilation between OSN Auto and OSN OFF at +4 dB SNR (measured at visit 3), as calculated via Growth Curve Analysis.
- Difference in overall pupil dilation between OSN Auto and OSN ON at +4 dB SNR (measured at visits 1 or 2), as calculated via Growth Curve Analysis.
- Difference in SSQ scores between Ponto 4 after 1 month field trial and own device.
- Difference in SSQ scores between Ponto 4 after 3 months field trial and own device.
- Difference in SSQ scores between Ponto 4 after 1-month field trial and after 3-months field trial.
- Correlation between peak pupil dilation and speech recognition scores.

- Number of test subjects preferring Ponto 4.
- Sound scenarios for which test subjects significantly prefer Ponto 4 over own device.
- Difference in dB between aided thresholds and BC in-situ thresholds –i.e., remaining air-bone gap (also known as BC gain or effective gain).

7.1.3 **Tertiary endpoints**

- Difference in NfR scores with Ponto 4 after field trial and own device.
- Correlation between NfR scores and pupil dilation with Ponto 4 after field trial.
- Difference in overall pupil dilation (intercept term) between Visit 1-2 and Visit 3 for the contrast OSN Auto vs. OSN OFF.
- Difference in peak pupil dilation between Visit 1-2 and Visit 3 for the contrast OSN Auto vs. OSN OFF.
- Difference in the following parameters between Visit 1-2 and Visit 3 for the pupil curves obtained with OSN Auto and OSN OFF: rate of growth/decay (linear term), changes in the rate of growth/decay (quadratic term), and the steepness of the curve around inflection points (cubic term).
- Difference in speech recognition scores between Visit 1-2 and Visit 3 for OSN Auto and OSN OFF.
- Correlation between pupil dilation and the patient's PTA and characteristics (e.g., age, unilateral/bilateral implantation).
- Correlation between speech recognition scores and the patient's PTA and characteristics (e.g., age, unilateral/bilateral implantation).

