7.3. Investigational device(s) and comparators

This is a post market study and the devices used in this study are CE marked. The test subjects' own devices will only be used as a reference device for the questionnaires (SSQ, NfR, preference). For the laboratory testing and for the field-trial period, Ponto 4 sound processors will be used. The following devices (and item numbers) will be used:

Name	Amount	Part number (color)	Description
Ponto 4	60	186777 (CBE) 186778 (TC) 186779 (SIL) 186780 (STG) 186781 (CNB) 186782 (DBL)	Oticon Medical BAHS Sound Processor. Released in 2019.

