APPENDIX A: ALL TEST CONDITIONS

It is estimated that testing one list will take about 8 minutes. For time estimate per person/ visit please see appendix B.

Condition	Visits 1	Visit 2	Visit 3	SNRs [dB SNR]	Total no. lists	Baseline [s]	Estimated time [min]
Training lists 1	X		X	+4 (OSN OFF) -4 (OSN ON)	2	Silence: 3 s Noise: 3 s	16
Training list 2		X		+4 (OSN OFF)	1	Silence: 3 s Noise: 3 s	8
OSN OFF	X	X		-8, -4, 0, +4, +8	5	Silence: 3 s Noise: 3 s	40
OSN ON	X	X		-8, -4, 0, +4, +8	5	Silence: 3 s Noise: 3 s	40
OSN Auto	X	X	X	+4	1	Silence: 2 s Noise: 6 s	8
OSN OFF			X	+4	1	Silence: 2 s Noise: 6 s	8

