APPENDIX B: BALANCED DESIGN ACROSS VISITS AND TIME ESTIMATE**VISITS 1 and 2**

- Subjects with **even ID number**, will perform

Visit 1 as follows:

- 2 training lists
- 6 test lists

Hence, 8 lists will be tested in total for a total testing time of 64 minutes. About 1 h 25 min should be taken into account to conduct pupillometry at Visit 1 (including breaks).

Visit 2 as follows:

- 1 training lists
- 5 test lists

Hence, 6 lists will be tested in total for a total testing time of 48 minutes. About 1 h 05 min should be taken into account to conduct pupillometry at Visit 2 (including breaks).

- Subjects with **odd ID number**, will perform

Visit 1 as follows:

- 2 training lists
- 5 test lists

Hence, 7 lists will be tested in total for a total testing time of 56 minutes. About 1 h 15 min should be taken into account to conduct pupillometry at Visit 1 (including breaks).

Visit 2 as follows:

- 1 training lists
- 6 test lists

Hence, 7 lists will be tested in total for a total testing time of 56 minutes. About 1 h 15 min should be taken into account to conduct pupillometry at Visit 2 (including breaks).

Visit 1 (even ID no.); Visit 2 (odd ID no.)										
	OSN ON					OSN OFF				
SNRs (dB)	-8	-4	0	4	8	-8	-4	0	4	8
Training (fixed order)		X*							X	
Test -8,0,8 (Randomized order)	X		X		X	X		X		X

* Only to be performed at Visit 1

Visit 1 (odd ID no.); Visit 2 (even ID no.)

	OSN ON					OSN Auto	OSN OFF				
SNRs (dB)	-8	-4	0	4	8	4	-8	-4	0	4	8
Training (fixed order)		X*									X
Test -4, 4 (Randomized order)		X		X		X		X		X	

* Only to be performed at Visit 1

Additionally, the following applies:

- The first OSN setting (ON or OFF) at visit 1 and 2 will be balanced between subjects (50% of the subjects will start with OSN ON and 50% of the subjects will start with OSN OFF – see Figure 1).
- The presentation order of SNRs will be randomized within each OSN setting.
- The OSN Auto condition will be presented either at Visit 1 or at Visit 2 – in between the two other settings (see Figure 1).
- The training for Visit 1 is performed in a fixed order: first +4 dB SNR with OSN OFF (relatively easy condition and condition used for screening), then -4 dB SNR with OSN ON (relatively more difficult condition).

VISIT 3

- At the third visit, 4 lists will be tested in total (including training) for a total testing time of 32 minutes. About 45 minutes should be taken into account to conduct pupillometry at the third visit (including breaks).

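### The own-device SSQ and NfR are listed after Ponto 4 has been fitted and tested at Visit 1, so the only baseline for two secondary SSQ comparisons and one exploratory NfR comparison can be affected by the new device

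*Combined protocol and SAP*

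**What the plan says.** Section 8.1 sets out Visit 1 as a list of seven items. After information, consent and demographics come "Fitting of Ponto 4 is performed (OSN ON, OSN OFF, OSN Auto" and then "Pupillometry during a speech-in-noise test is performed (training, OSN ON, OSN OFF, OSN Auto – see Figure 1". The seventh and last item is "All subjects fill in the SSQ and NfR questionnaires in relation to their own device (reference device".

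The device heard in the laboratory is always the new one. Section 7.3 says "For the laboratory testing and for the field-trial period, Ponto 4 sound processors will be used" and keeps the patient's own device only as a reference for the questionnaires.

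Appendix B gives the length of the session. For even IDs at Visit 1, "8 lists will be tested in total for a total testing time of 64 minutes"; for odd IDs it is 7 lists and 56 minutes. With breaks, the slots are about 1 h 25 min and 1 h 15 min.

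Section 7 and Table 1 place the own-device SSQ and NfR at Visit 1 without an order inside the visit. These scores are collected once. They are the reference for the 1-month SSQ endpoint and for "Difference in SSQ scores between Ponto 4 after 3 months field trial and own device", both in Section 7.1.2, and for the NfR difference in Section 7.1.3, which Section 6.3 classes as exploratory.

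**The concern.** A patient who follows the list rates the old device after being fitted with its successor and listening through it for about an hour. The rating may then be a comparison with the new device rather than a report on the old one. The plan describes blinding to the test condition, not to the device, and Section 5 tells patients that they may keep Ponto 4.

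Tiredness is a second route. Section 5 expects it from listening to and repeating speech in noise, and Section 7 names fatigue as a reason for keeping OSN settings at one SNR within one visit. The questionnaires have no similar protection.

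At stake is the interpretation of two secondary SSQ endpoints and one exploratory NfR endpoint. These are before-after comparisons without a control group, so the mixed-model ANOVA or paired test in Section 12 cannot separate a shifted baseline from a device effect. Once Ponto 4 has been heard, an unexposed baseline cannot be recovered.

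**Working it through.** **1. Testing time before the questionnaires, if the list is followed.** Inputs: from Appendix A, "It is estimated that testing one list will take about 8 minutes"; from Appendix B, 2 training lists plus 6 test lists (even IDs) or 5 test lists (odd IDs).

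- Even IDs: (2 + 6) × 8 = 64 min.
- Odd IDs: (2 + 5) × 8 = 56 min.

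Both reproduce the figures in Appendix B. Fitting time comes on top.

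**2. Which comparisons carry a baseline shift.** Let B be the own-device score free of influence, and P1 and P3 the Ponto 4 scores at 1 and 3 months. Let h be the shift from having heard Ponto 4, f the shift from testing just before the Visit 1 questionnaires, and g the shift from testing just before the Visit 3 questionnaires. The observed baseline is B + h + f.

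- SSQ, 1 month minus own device: P1 − (B + h + f) = (P1 − B) − h − f. The 1-month SSQ is completed at home, so nothing offsets f.
- SSQ, 3 months minus own device: (P3 + g) − (B + h + f) = (P3 − B) − h − (f − g). Section 8.1 lists the Visit 3 questionnaires after pupillometry (4 × 8 = 32 min), audiometry and sound-field testing. Tiredness therefore partly cancels; h does not.
- NfR, Visit 3 minus own device: the same form as the 3-month SSQ.
- Preference: one comparative questionnaire at Visit 3, which uses no Visit 1 score.
- Primary endpoint and other OSN contrasts: all measured with Ponto 4; B does not appear.

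**3. Size.** The documents give no mean, SD or expected shift for SSQ or NfR, so h, f and g cannot be estimated. To show sensitivity only, assume 30 pairs, a two-sided paired t-test at 5%, no true device difference, and a net shift of δ SD of the paired difference. The rejection probability is that of a noncentral t with 29 degrees of freedom and noncentrality δ√30 (for δ = 0.2, 0.2 × 5.48 = 1.10).

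| Net shift δ (SD of paired difference) | Probability of a significant result |
|---|---|
| 0 | 5.0% |
| 0.1 | 8.3% |
| 0.2 | 18.5% |
| 0.3 | 35.5% |
| 0.4 | 56.3% |
| 0.5 | 75.4% |

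The result is the same for a shift in either direction. The paired t-test stands in for the planned mixed-model ANOVA of SSQ.

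For NfR, one item of 11 is worth 100 / 11 = 9.1 points. That is scale arithmetic and no evidence that an answer would change.

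**The case against.** - **The order is inferred.** Section 8.1 is an outline, and nothing says that its items bind in sequence. For Visit 3, Section 7 mentions the questionnaires and then, as the final step, audiometry, while Section 8.1 lists audiometry first. This stands: a reader might infer that the plan mandates a contaminated baseline, but it only lists that order and leaves it open. Even so, a site following the outline would collect the baseline last, and a site that did not could vary the order between patients.
- **The direction is unknown.** Before the questionnaires, patients hear Ponto 4 at SNRs down to −8 dB (even IDs) or −4 dB (odd IDs), with OSN OFF in 4 of 8 or 3 of 7 lists. A hard session could make the familiar device look better and understate the benefit. Own-device ratings also rest on at least 6 months of daily use of a Ponto processor. This stands: the documents do not support reading the order as inflating the benefit of Ponto 4.
- **Tiredness is present at both ends of the 3-month comparisons.** This stands in part. The two sessions differ in length and content, and the 1-month SSQ has no testing before it.
- **NfR asks yes/no questions about fatigue from work**, not about tiredness at the moment. This stands; the risk is weaker there.
- **Reordering has a price.** Screening uses BC in-situ thresholds and the first training list at Visit 1, so some patients would complete questionnaires and then fail. Questionnaire burden would also precede pupillometry. Both are true and small: the primary ON–OFF contrast is made within one visit with balanced starting order, so the burden falls on both settings alike.
- **Reordering leaves an uncontrolled comparison without device blinding.** True, but it removes one avoidable source of bias.

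**Conclusion.** The point holds within limits. As listed, the only own-device baseline is collected after the Ponto 4 fitting and 56–64 minutes of Ponto 4 testing, and no provision places it earlier. Two secondary SSQ comparisons and one exploratory NfR comparison can be affected by prior exposure to the new device; the 1-month SSQ comparison is also exposed to tiredness that nothing offsets. A reader might infer that every comparison of Ponto 4 with the own device is compromised. That is not supported, because the preference endpoints use no Visit 1 score.

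The documents establish the possibility of bias, not its presence, sign or size. The percentages in the table rest on assumed shifts and 30 complete pairs, and do not estimate what happens in this trial. The point has no bearing on the sample size. It is worth correcting because an unexposed baseline cannot be obtained later and the correction costs little.

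**What to change.** - In Section 8.1, state that the own-device SSQ and NfR are completed after consent and before Ponto 4 is fitted or heard.
- At Visit 3, place the SSQ and NfR before pupillometry, so that both ends of the comparison are rated under like conditions. This also brings the 3-month SSQ closer to the 1-month SSQ completed at home.
- For patients already tested, report the order actually followed and name it as a limitation of the SSQ and NfR comparisons.

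Cost: a change of order within existing visits, with no new assessment and no change in sample size. Patients who then fail the Visit 1 screen will have completed two questionnaires for nothing. Some burden moves ahead of pupillometry; a break can be given, and it applies equally to the OSN settings compared within the visit.

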8.2. Clinical assessments**8.2.1. Pure tone audiogram**

Detection of pure tones delivered by the audiometer via air-conduction and bone conduction, as used for measuring conventional audiometry. Tested frequencies for air-conduction are: 250 Hz, 500 Hz, 750 Hz, 1 kHz, 2 kHz, 3 kHz, 4 kHz, 6 kHz, 8 kHz. Tested frequencies for bone-conduction are: 500 Hz, 1 kHz, 2 kHz, 3 kHz, 4 kHz.

8.2.2. Sound field audiometry

Aided threshold will be measured in order to calculate remaining air-to-bone gap (also called BC gain or effective gain).

The Ponto 4-45 will be programmed with DFC OFF, directionality mode Omni and noise reduction OFF.

The measurement will be conducted in a sound field setup with the loudspeaker placed 1 meter in front of the test person (0° azimuth), with warble tones at frequencies 250-, 500- 750-, 1000-, 1500-, 2000-, 3000-, 4000-, 6000- and 8000 Hz.

8.2.3 Fitting

Fitting will be performed by a trained audiologist at Queen Elizabeth Hospital. The fitting will follow the recommended fitting flow from the manufacturer. The Ponto 4 will be fitted with the NAL-NL1 rationale; a feedback measurement as well as a BC in-situ audiometry measurement will be conducted. Further and individualized fine tuning will not be performed, for comparison reasons, unless it is absolutely necessary. See Table 2 for an overview of the settings for each condition: OSN ON, OSN OFF, OSN Auto.

Table 2 Overview of Ponto 4-45 settings for OSN ON, OSN OFF, OSN Auto.

	OSN ON	OSN OFF	OSN Auto
Feedback measurement	X	X	X
DFC	As prescribed	As prescribed	As prescribed
BC in-situ audiometry	Copied from OSN Auto	Copied from OSN Auto	X

Fine tuning	No fine tuning	No fine tuning	Preferably no fine tuning
OpenSound Navigator: -Directionality settings -Open Sound transition	Full Directional Very High*	Omni N/A	Open Automatic Medium
Noise reduction complex	-9 dB	OFF	-7 dB (default)
Noise reduction simple	-3 dB	OFF	0 dB (default)

*When fitting the 'OSN ON – condition' the following steps will be followed:

1. Directionality settings will be set to Open Automatic;
2. Transition will be set to Very High;
3. Directionality settings will be set to Full Directional.

8.3. Test setup and materials

8.3.1 Pupillometry

The setup for this study consists of five loudspeakers positioned at a distance of 1 m from the test participant (see Figure 1). An eye tracking camera will be placed in front of the test person approximately 60 cm from the eyes. The eye-tracking camera is the Pupil Labs. The camera will track the pupil size of the test person during the speech-in-noise task.

UK English sentences will be presented in a 4-talker babble background noise. The loudspeaker at the 0° azimuth position will playback the target speech signal. The remaining 4 loudspeakers will each playback one of the 4 overlapping babble talkers at +/-90° and +/-150° azimuth. Additionally, unmodulated speech-shaped noise (SSN) was added to the 4-talker babble to simulate a diffuse noise environment and to trigger the automatic control of the NR algorithms (as in Wendt et al., 2017). The SSN was added to the two competing talkers presented from the back at ±150° with an SNR of -1.8 dB (i.e., the SSN was presented at a lower level than the babble).

Each trial will start with a short silence, followed by a baseline with noise (see silence and baseline durations in Appendix A). The sentence will start after the baseline. After sentence offset, the participant will need to wait for 3 seconds before repeating the sentence (retaining window).

[figure not shown]

Figure 2 Loudspeaker and camera setup used for the speech-in-noise test. The participant will wear one or two Ponto 4 on abutment.

8.3.2 Speech recognition test

Speech recognition scores (% correct) will be measured for the speech-in-noise task over a broad range of SNRs from -8 dB to +8 dB. See the details of the target sentences and noise in the previous section. The overall masker level (4-talker babble and SSN) is kept constant at 70 dB SPL to ensure that the noise would not become too loud at low SNRs. The level of the speech is adjusted consequently for each tested SNR.

8.3.3 Speech, Spatial, and Qualities of Hearing (SSQ) questionnaire

The Speech, Spatial and Qualities of Hearing Scale (SSQ) is designed to measure a range of hearing disabilities across several domains (Gatehouse and Noble, 2004). Particular attention is given to speech perception in a variety of competing contexts, and to the directional, distance and movement components of spatial hearing. In addition, the abilities both to segregate sounds and to attend to simultaneous speech streams are assessed, reflecting the reality of hearing in everyday life. Qualities of hearing experience include ease of listening, and the naturalness, clarity and identifiability of different speakers, different musical pieces and instruments, and different everyday sounds. Appendix 2 in Gatehouse and Noble (2004) gives the complete text of each item. Each item is scored from 0 to 10, with larger values always indicating greater ability.

8.3.4 Need for Recovery (NfR) questionnaire

The NfR questionnaire was originally designed and validated in Dutch and then translated into UK English (van Veldhoven and Broersen, 2003; de Croon et al., 2006). The NfR scale is an 11-item scale assessing the effects of fatigue caused by work (e.g., "I find it hard to relax at the end of a working day"). Possible responses are "yes" or "no". The total NfR score is the number of "yes" responses divided by the total number of items, presented as a percentage (i.e., range 0–100). The higher the score, the greater the NfR felt by the respondent.

It has been shown that a negative correlation exists between NfR scores and peak pupil dilation (Wang et al., 2018), suggesting that fatigued individual allocate less effort to perform a speech recognition in noise task. In this study, NfR will be collected in relation to both the reference device and Ponto 4, in an attempt to gain more insights into interindividual differences in PPD and factors

	Title Assessing listening effort at different signal-to-noise ratios in bone-anchored users	Document no Doc-00064398	Revision 1	Page 20(33)
---	---	------------------------------------	----------------------	-----------------------

influencing acclimatization.

8.3.5 Preference questionnaire

The Preference questionnaire evaluates the preference for test device (Ponto 4) and reference device (own Ponto device) in different sound scenarios, for example: speech-intelligibility in quiet, speech-intelligibility in background noise in small and bigger groups. The questionnaire uses a comparative scale, where users rate whether they prefer: "The reference device much better", "The reference device somewhat better", "No preference", "The test device (Ponto 4) somewhat better", "The test device (Ponto 4) much better".

